2.2.4.2.2. Population Pharmacokinetics

PK analyses in male and female AD patients and healthy volunteers indicated that systemic exposure (AUC) of abrocitinib in the extremes of body weight (52 kg to 111 kg) was similar (within 20%) to that of a 70 kg individual. The enzymatic activity of CYP enzymes is reduced in patients with atopic dermatitis due to chronic inflammation. Patients with inflammatory disease had approximately 30% higher steady-state abrocitinib exposures compared to healthy volunteers. The observed metabolite/parent ratios of each of the metabolites in AD patients are similar to those observed in healthy subjects. Adolescent patients, including those with lower body weight (down to 25 kg), have similar exposures of abrocitinib compared to adults. There are no clinically relevant differences in exposure for abrocitinib or active moiety in adolescents ≥ 25 kg compared with adult AD patients. Based on population PK analyses, atopic dermatitis, age, sex, body weight, and race did not have a clinically meaningful effect on exposures of abrocitinib and active moiety.

2.3. Benefit/Risk Assessment

Abrocitinib is not expected to provide any clinical benefit to healthy participants. This study is designed primarily to generate PK, safety, and tolerability data for further clinical development of abrocitinib. Caffeine, efavirenz, and omeprazole are used as probes of CYP1A2/2B6/2C19, respectively, which PK may be affected by abrocitinib. A study that shows lack of DDI when these substrates are co-administered with abrocitinib improves

confidence in the co-administration of abrocitinib with a wide variety of commonly used drugs.

More detailed information about the known and expected benefits and risks and reasonably expected AEs of abrocitinib may be found in the IB, which is the SRSD for this study.

3. OBJECTIVES AND ENDPOINTS

Objectives	Endpoints
Primary:	Primary:

To estimate effect of multiple dose abrocitinib on the PK of single, oral doses of caffeine, efavirenz and omeprazole in healthy participants.	
AUC_{inf} (if applicable, otherwise AUC_{last}) and of caffeine, efavirenz and omeprazole.
Secondary:	Secondary:

To evaluate the safety and tolerability of abrocitinib when co administered with single doses of caffeine, efavirenz and omeprazole.	
Vital signs, laboratory tests and AEs.
CCl [REDACTED] [REDACTED] [REDACTED]	[REDACTED] [REDACTED] [REDACTED]

4. STUDY DESIGN

4.1. Overall Design

This is a Phase 1, open-label, multiple dose, single fixed-sequence, 2-period study to evaluate the effect of abrocitinib on the PK of caffeine, efavirenz and omeprazole in healthy adult participants. A total of approximately 13 healthy male and/or female participants will be enrolled in the study to obtain at least 12 evaluable participants who complete the study. Participants who withdraw from the study or are considered non-evaluable may be replaced at the discretion of the sponsor.

Participants will be screened within 28 days of the first dose of study intervention. Participants will have a phone contact 3 days prior to Day 1 dosing (Day -3) in Period 1 as a reminder to abstain from caffeine-containing products. Participants will be admitted to the CRU at least 24 hrs prior to Day 1 dosing (Day -1) in Period 1. Participants will remain in the CRU for a total of 15 days and 14 nights.

In Period 1, all the participants will receive single doses of probe drugs, including caffeine 100 mg, efavirenz 50 mg and omeprazole 10 mg, together on Day 1. The Day 1 of Period 2 begins on the fourth day following the start of Period 1. The predose and up to 24 hours post

dose PK samples will be analyzed for caffeine, efavirenz, and omeprazole; while the 48 and 72 hours post dose PK samples will be analyzed for efavirenz PK only. After 3 days of PK sampling in Period 1, Period 2 will immediately follow with no washout.

In Period 2, participants will receive abrocitinib 200 mg QD on Day 1-10. On Period 2 Day 2, participants will receive single dose of omeprazole 10 mg alone within approximately 5 minutes after administration of a 200 mg dose of abrocitinib in the morning. PK samples for omeprazole concentration measurement will only be collected from predose and up to 8 hours post dose. Participants will receive single doses of the probe drugs (caffeine 100 mg, efavirenz 50 mg and omeprazole 10 mg together) again on Day 8, and omeprazole 10 mg alone on Day 2, within approximately 5 minutes after administration of abrocitinib 200 mg on the morning of the respective day. The predose and up to 24 hours post dose PK samples will be analyzed for caffeine, efavirenz, and omeprazole; while the 48 and 72 hours post dose PK samples will be analyzed for efavirenz PK only.

Participants will have a telephone contact between 28-35 calendar days after the last administration of the investigational product.

The total planned duration of participation, from the Screening visit to the last Follow-up phone call, is approximately up to 11 weeks.

Table 2. Treatment Flow Diagram

Treatment	Period 1		Period 2				
	Day 1	Day 2-3	Day 1	Day 2	Day 3-7	Day 8	Day 9-11
Abrocitinib 200 mg QD			X	X	X	X	X
Caffeine 100 mg SD	X					X	
Efavirenz 50 mg SD	X					X	
Omeprazole 10 mg SD	X			X		X	

4.2. Scientific Rationale for Study Design

Inhibition and induction of the CYP1A2/2B6/2C19 enzymes by abrocitinib were assessed in HLM and human hepatocytes. Abrocitinib was a weak TDI of CYP2C19 and a weak inducer of CYP1A2/2B6/2C19 enzymes. The purpose of the study is to evaluate the effect of abrocitinib on the in vivo PKs of sensitive CYP1A2, 2B6 and 2C19 substrates, caffeine, efavirenz, and omeprazole. The probe drugs used in this study, caffeine, efavirenz, and omeprazole are a subset of the Basel cocktail, which has been validated for simultaneous phenotyping of CYP isoforms², and can be used without additional validation.

Multiple dose administration of the investigational drug for a minimum of 7 days is generally recommended to evaluate its induction effect on enzyme activity, as inducers can take several days to exert their effects. While the onset of inhibition effect on CYP enzymes by potential inhibitors is relatively quick. Therefore, caffeine, efavirenz, and omeprazole will be given on Day 8 during the 10 days of abrocitinib QD dosing to assess the potential induction effect of abrocitinib on CYP1A2/2B6, and net effect of TDI and induction on CYP2C19. Omeprazole

will be given on Day 2 to assess the TDI effect of abrocitinib on CYP2C19, with only sparse PK samples to be taken for future exploration using PBPK modeling approach.

Efavirenz has a long $t_{1/2}$ ranging from 52-76 hours. PK samples collected up to 72 hr may not support $t_{1/2}$ and AUC_{inf} calculation, therefore, partial $AUC_{0-72 \text{ hr}}$ (AUC_{last}) may be used as the primary endpoint for efavirenz. At a single dose of 50 mg, efavirenz is not expected to induce or inhibit (competitively or mechanism based) any metabolizing system².

PK samples collected up to 24 hr is sufficient to capture the full PK profiles of caffeine and omeprazole considering their relatively short half-lives of approximately 5 hr and 1-4 hr, respectively.

CCI

[figure not shown]

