9.3.1.2. Derivation of Pharmacokinetic Parameters

PK parameters will be derived from the plasma concentration time profiles as shown in Table 3.

Table 3. Plasma Pharmacokinetic Parameter Definitions

Parameter	Definition	Method of Determination
AUC _{last}	area under the concentration-time curve from time 0 to time of the last measureable concentration	Linear/Log trapezoidal rule
AUC _{inf}	area under the concentration-time curve from time 0 to infinity	AUC _{last} + (C _{last} [*] /k _{el}), where C _{last} [*] is the predicted plasma concentration at the last quantifiable time point estimated from the loglinear regression analysis, and k _{el} is the terminal phase rate constant calculated by a linear regression through at least 3 data points in the terminal phase of the loglinear concentration time curve
CC		
CC		
CCI		
CCI		
C		
C		
I		

Natural log-transformed parameters (AUC_{inf}, AUC_{last} CCI) will be analyzed using a mixed effect model with treatment as a fixed effect and subject as a random effect. Estimates of the adjusted mean differences (Test-Reference) and corresponding 90% CIs will be obtained from the model. The adjusted mean differences and 90% CIs for the differences will be exponentiated to provide estimates of the ratio of adjusted geometric means (Test/Reference) and 90% CI for the ratios. The Test and Reference treatments to estimate the treatment difference for each of the study objectives are as follows:

- Objective 1: caffeine 100 mg (Period 1, Day 1) will be the Reference treatment; abrocitinib 200 mg + caffeine 100 mg (Period 2, Day 8) will be the Test treatment.
- Objective 2: efavirenz 50 mg (Period 1, Day 1) will be the Reference treatment; abrocitinib 200 mg + efavirenz 50 mg (Period 2, Day 8) will be the Test treatment.
- Objective 3: omeprazole 10 mg (Period 1, Day 1) will be the Reference treatment; abrocitinib 200 mg + omeprazole 10 mg (Period 2, Day 8) will be the Test treatment.

Residuals from the model will be examined for normality and the presence of outliers via visual inspection of plots of residuals vs predicted values and normal probability plots of residuals but these will not be included in the CSR. If there are major deviations from normality or outliers, then the effect of these on the conclusions will be investigated through alternative transformations and/or analyses excluding outliers. Justification for any alternative to the planned analysis will be given in the report of the study.

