## 6.3. Other Endpoints

### 6.3.1. PK Endpoints

Blood samples for PK analysis of *caffeine*, *efavirenz* and *omeprazole* will be taken according to the Schedule of Activities given in the protocol.

The following PK parameters will be calculated for *caffeine*, *efavirenz* and *omeprazole* (if possible) from the concentration-time data using standard noncompartmental methods:

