## 8.2. Statistical Analyses

*Natural log-transformed parameters ( $AUC_{inf}$ ,  $AUC_{last}$ , CCI) will be analyzed using a mixed effect model with treatment as a fixed effect and subject as a random effect. Estimates of the adjusted mean differences (Test-Reference) and corresponding 90% CIs will be obtained from the model. The adjusted mean differences and 90% CIs for the differences will be exponentiated to provide estimates of the ratio of adjusted geometric means (Test/Reference) and 90% CI for the ratios. The Test and Reference treatments to estimate the treatment difference for each of the study objectives are as follows:*

- *Objective 1: caffeine 100 mg (Period 1, Day 1) will be the Reference treatment; abrocitinib 200 mg + caffeine 100 mg (Period 2, Day 8) will be the Test treatment.*
- *Objective 2: efavirenz 50 mg (Period 1, Day 1) will be the Reference treatment; abrocitinib 200 mg + efavirenz 50 mg (Period 2, Day 8) will be the Test treatment.*
- *Objective 3: omeprazole 10 mg (Period 1, Day 1) will be the Reference treatment; abrocitinib 200 mg + omeprazole 10 mg (Period 2, Day 8) will be the Test treatment.*

*Residuals from the model will be examined for normality and the presence of outliers via visual inspection of plots of residuals vs predicted values and normal probability plots of residuals but these will not be included in the CSR. If there are major deviations from normality or outliers, then the effect of these on the conclusions will be investigated through alternative transformations and/or analyses excluding outliers. Justification for any alternative to the planned analysis will be given in the report of the study.*

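### Does the plan leave a gap by giving the Period 2 Day 2 omeprazole profile no visible Test/Reference comparison?

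*Protocol*

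**What the plan says.** Protocol section 4.2 assigns the two Period 2 omeprazole doses different tasks. The Day 8 dose measures the "net effect of TDI and induction on CYP2C19". The Day 2 dose is given "to assess the TDI effect of abrocitinib on CYP2C19, with only sparse PK samples to be taken for future exploration using PBPK modeling approach". Section 4.1 limits the Day 2 profile: "PK samples for omeprazole concentration measurement will only be collected from predose and up to 8 hours post dose". Protocol Table 1 lists five Day 2 samples, at 0, 1, 3, 6 and 8 h; these times are also sampled on Period 1 Day 1 and Period 2 Day 8, where omeprazole is followed to 24 h.

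The primary objective in protocol section 3 is "To estimate effect of multiple dose abrocitinib on the PK" of the three probes. For omeprazole, protocol 9.3.1.2 fixes the reference day, "Objective 3: omeprazole 10 mg (Period 1, Day 1) will be the Reference treatment", and SAP 8.2 repeats the test day, "abrocitinib 200 mg + omeprazole 10 mg (Period 2, Day 8) will be the Test treatment". The example code in SAP Appendix 1 has two treatment levels: A (probes alone) and B (probes with abrocitinib). SAP 6.3.1 plans omeprazole parameters where they can be calculated and names no day.

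**The concern.** Every participant takes an extra omeprazole dose and gives five samples for a stated question, early time-dependent inhibition (TDI) of CYP2C19, and no visible estimate answers it. Day 8 alone cannot separate absence of effect from inhibition offset by induction, so a Day 2 ratio looks like useful information left unused.

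There is also a possible mix-up. Day 2 and Day 8 omeprazole are both in Period 2 and both given with abrocitinib, and the SAP shows no treatment label for Day 2. AUClast is defined as the "area under the concentration-time curve from time 0 to time of the last measureable concentration", so a Day 2 value stops at 8 h while the others can run to 24 h. If Day 2 records entered level B, or were read against a 24 h AUClast, the omeprazole ratio would be biased downwards.

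**Working it through.** **1. Do the passages conflict?** Section 4.2 states both the question for Day 2 and the method: sparse sampling, PBPK modelling, later. Section 3 asks about multiple-dose abrocitinib; Day 8 is the eighth daily dose and Day 2 only the second. Protocol 9.3.1.2 and SAP 8.2 then contrast Day 8 with Period 1 Day 1. Purpose, objective and contrast agree.

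**2. Can Day 2 enter the primary contrast?** Both documents define the omeprazole Test treatment by period and day, Period 2 Day 8. A programmer who follows them leaves Day 2 out. The code in Appendix 1 is introduced as an example and does not override that definition.

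**3. How large would a mix-up be?** With mono-exponential decline and no drug effect, AUC to 8 h over AUC to 24 h is (1 − 2^(−8/t½)) / (1 − 2^(−24/t½)). For the 1–4 h half-life in section 4.2 this is 0.996, 0.938 and 0.762 at 1, 2 and 4 h. The truncation matters at 4 h, but it arises only if the stated Test day is ignored.

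**4. The plan's own precision.** Protocol 9.5 gives n = 12, a within-participant SD of 0.25 for ln AUCinf of omeprazole, and 80% coverage probability. Half-width = t(0.95, 11) × SD × √(2/12) × √(χ²(0.80, 11)/11) = 1.7959 × 0.25 × 0.4082 × 1.1533 = 0.2114, as stated. SDs of 0.13 and 0.24 give 0.1099 and 0.2029, also as stated.

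**5. What would a Day 2 / Day 1 ratio show?** Assume AUC0–8 on the five shared times, unchanged volume and mono-exponential decline. For a fractional clearance loss f the true ratio is [1/(1 − f)] × (1 − 2^(−8(1−f)/t½)) / (1 − 2^(−8/t½)). The chance that the 90% CI lies wholly above 1 comes from the noncentral t with 11 df and noncentrality ln(ratio) / (SD × √(2/12)). The documents give no SD for a five-point AUC0–8, so 0.25 is carried over and 0.40 is an assumed upper value. Entries are for t½ = 1 / 2 / 4 h.

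| Clearance loss | AUCinf ratio | AUC0–8 ratio | Chance, SD 0.25 | Chance, SD 0.40 |
|---|---|---|---|---|
| 10% | 1.11 | 1.11 / 1.09 / 1.06 | 0.24 / 0.19 / 0.13 | 0.15 / 0.12 / 0.09 |
| 20% | 1.25 | 1.24 / 1.19 / 1.12 | 0.63 / 0.48 / 0.26 | 0.34 / 0.26 / 0.16 |
| 30% | 1.43 | 1.40 / 1.31 / 1.18 | 0.93 / 0.79 / 0.46 | 0.62 / 0.45 / 0.25 |

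Section 4.2 calls abrocitinib a weak time-dependent inhibitor, so the upper rows are the relevant ones. The study sets no hypotheses, so a CI above 1 is only a yardstick here.

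**6. What would a null ratio exclude?** At SD 0.25 an observed ratio of 1 has a CI of exp(±0.2114) = 0.81 to 1.24. Solving the ratio formula for 1.235 gives clearance losses of about 20%, 24% and 37% at t½ 1, 2 and 4 h. At SD 0.40 the half-width is 0.338, the CI is 0.71 to 1.40, and the bounds are about 30%, 37% and 58%.

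**7. How sturdy is a five-point AUC0–8?** In a one-compartment oral model with assumed absorption rates of 0.5–3 per h, lags of 0–2 h and half-lives of 1–4 h, the five-point value ranges from 54% to 104% of the true AUC0–8. At an assumed absorption rate of 1.5 per h, a within-person lag shift of 0.5 to 1.0 h moves it by −14% to −30%, against −4% to −6% on the full sampling grid to 8 h. A chance shift in absorption can therefore exceed the effect sought.

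**The case for a change.** The strongest case for a change is that it costs almost nothing. The data are collected, the five times match across the three days, and a matched AUC0–8 removes the truncation problem. A separate label for Day 2 would settle how it is listed and summarised: SAP 8.2 sorts concentrations by period and nominal time and summarises them by treatment, and neither visibly separates Day 2 from Day 8.

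The labelling remark stands as a point of clarity. No visible text names a treatment for Day 2 in the by-treatment summaries and plots. It does not reach the primary analysis, where the Test day is named, and all concentrations are listed in any case.

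The added ratio is a matter of preference. Besides its low yield, it would need an AUC0–8 ratio for Day 8 as comparator. That second Day 8 ratio is attenuated: at a 4 h half-life and 30% clearance loss it would be 1.18, against 1.43 for AUCinf. It would also rest on the statement in protocol 4.3 that the probes do not interact, because Day 2 omeprazole is given without caffeine and efavirenz. Statisticians could reasonably differ on whether to report it.

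Nor can absence be shown. The exploratory objectives and parts of the parameter and analysis sections are redacted in both documents, and a Day 2 endpoint or summary would sit there.

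**Conclusion.** The concern does not hold. The plan states why Day 2 is sampled and how the data will be used, the multiple-dose objective is met by the Day 8 contrast, and the named Test day keeps Day 2 out of it. The omeprazole estimate and its planned precision of ±0.2114 on the log scale are unaffected.

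The unused information is small for the weak inhibition the protocol describes: a 0.13 to 0.63 chance of a CI above 1 at 10–20% clearance loss with SD 0.25, and 0.09 to 0.34 with SD 0.40. These figures assume mono-exponential decline, unchanged volume, 12 evaluable participants and an SD borrowed from AUCinf. The conclusion does not depend on them; it follows from the stated purpose of the Day 2 samples and the explicit definition of the Test treatment.

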2.2.2. Nonclinical Pharmacokinetics and Metabolism

Plasma profiling from the [¹⁴C]abrocitinib human mass balance study indicated unchanged abrocitinib as the most prevalent circulating species (26%), with 3 major and more polar

mono-hydroxylated metabolites identified. M1, M2, and M4 are not unique to humans, and were shown to have sufficient exposures at NOAEL doses in rats (rat/human AUC₂₄ ratios ≥ 1) relative to the projected highest therapeutic human dose of 200 mg daily.

In vitro and in vivo metabolite profiling suggested that the primary clearance mechanism for abrocitinib was CYP-mediated oxidation, with CYP2C19 the primary contributor at approximately 50%. CYP metabolism played a minor role (<25%) in the clearance of metabolites M1, M2 and M4. Renal excretion of parent drug was limited in the mouse, rat and humans, while urinary excretion was the major route of elimination for M1, M2, and M4.

Abrocitinib, M1, M2, and M4 were not significant competitive inhibitors of CYP enzymes, but showed varying weak TDI activities versus CYP3A, CYP2C19 and CYP2D6.

Abrocitinib exhibited a weak potential to induce CYP1A2, CYP3A4 and CYP2B6. M1, M2, and M4 did not induce CYP3A4 enzyme activity or mRNA. M1 and M2 showed a weak potential to induce CYP1A2 and CYP2B6. Clinical results with midazolam as a victim indicated no significant risk of interaction through inhibition or induction of CYP3A after abrocitinib administration.

Abrocitinib, M1, M2, and M4 were not significant inhibitors of the major UGT enzymes or SULT enzymes. Clinical results with ethinyl estradiol as a victim indicated no significant risk of UGT or SULT inhibition by abrocitinib and its metabolites.

Abrocitinib was not a substrate for OATP1B1 or OATP1B3, nor inhibited these transporters. Abrocitinib did not inhibit OAT1, OCT2, or bile salt export pump, but inhibited OAT3, P-gp, BCRP, OCT1, MATE1, and MATE2K. M1, M2, and M4 did not inhibit P-gp, OCT2, and OAT1. M2 and M4 did not inhibit OATP1B1 and OATP1B3. M1, M2, and M4 inhibited BCRP, MATE1, MATE2K, and OAT3. Clinical results showed abrocitinib co-administration increased dabigatran exposure <2 fold, indicative of the inhibition of dabigatran etexilate efflux by P-gp, and showed no significant effect on the exposure of rosuvastatin (BCRP, OAT3 probe substrate) or metformin (OCT2, MATE1/2K, OCT1 probe substrate).

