9. STATISTICAL CONSIDERATIONS

Detailed methodology for summary and statistical analyses of the data collected in this study is outlined here and further detailed in a SAP, which will be maintained by the sponsor. The SAP may modify what is outlined in the protocol where appropriate; however, any major modifications of the primary endpoint definitions or their analyses will also be reflected in a protocol amendment.

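### Efavirenz left from the Period 1 dose is counted in the Period 2 Day 8 AUC, raising Test/Reference by about 4% to 11% if there is no induction and decay is mono-exponential

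*Protocol*

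**What the plan says.** On timing, Protocol section 4.1 states: "After 3 days of PK sampling in Period 1, Period 2 will immediately follow with no washout". It adds: "The Day 1 of Period 2 begins on the fourth day following the start of Period 1". The 50 mg efavirenz dose is given on Period 1 Day 1 and again on Period 2 Day 8. Protocol section 4.2 gives the half-life: "Efavirenz has a long $t_{1/2}$ ranging from 52-76 hours".

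On the endpoint, the primary measure is AUCinf where it can be estimated and AUClast otherwise. For efavirenz section 4.2 expects that AUC to 72 h may have to serve, because "PK samples collected up to 72 hr may not support" estimation of the half-life and AUCinf. Table 3 (section 9.3.1.2) defines AUClast as "area under the concentration-time curve from time 0 to time of the last measureable concentration", with no baseline subtraction. The comparison is Day 8 (Test) against Period 1 Day 1 (Reference), in a model with treatment fixed and subject random (SAP 8.2).

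On sampling, section 4.1 states for both periods: "The predose and up to 24 hours post dose PK samples will be analyzed for caffeine, efavirenz, and omeprazole". A Day 8 predose efavirenz concentration will therefore exist.

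On the expected effect, section 2.2.2 reports: "Abrocitinib exhibited a weak potential to induce CYP1A2, CYP3A4 and CYP2B6". CYP2B6 is the enzyme that efavirenz probes.

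**The concern.** Day 8 efavirenz concentrations are the sum of the new dose and whatever remains of the first. The Period 1 Reference has no such residue. Because every participant follows the same sequence, the extra exposure always falls on Test. It does not average out, and enrolling more participants would not reduce it.

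The direction matters. Induction of CYP2B6 would lower efavirenz exposure, and residue raises the observed ratio, so the bias works against the signal that the Day 8 dose is meant to detect. Protocol section 2.3 says that a finding of no interaction would support wide co-administration, so an estimate pushed towards 1 has consequences even without a formal test. The documents give no expected in vivo change in efavirenz AUC, so the share of a real effect that might be hidden cannot be stated.

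**Working it through.** **The plan's own figure first.** Half-width = t(0.95, 11) × SD × √(2/12) × √(χ²(0.80, 11)/11). With SD = 0.24 (Protocol 9.5), this is 1.796 × 0.0980 × √(14.63/11) = 0.2029, as stated.

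**Dose-to-dose interval.** Table 1 places the 72 h sample of Period 1 on Period 2 Day 1. Day 8 is seven days later: 72 + 7 × 24 = 240 h. The 15-day stay agrees: Day -1, three days of Period 1 and eleven of Period 2. In half-lives, 240/76 = 3.16 and 240/52 = 4.62.

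**Inflation with no induction.** With equal doses and mono-exponential decay, the residue's share of a dose's own AUC is r = 2^(−240/h), for AUC to 72 h and AUCinf alike. Coverage uses the noncentral t with 11 df and SE = 0.24 × √(2/12) = 0.0980. It assumes that the planning SD for ln AUCinf also applies to AUC to 72 h.

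| Half-life h | r | ln(1+r) | Share of 0.2029 | Coverage of nominal 90% CI |
|---|---|---|---|---|
| 52 h | 4.1% | 0.040 | 20% | 0.875 |
| 64 h | 7.4% | 0.072 | 35% | 0.821 |
| 76 h | 11.2% | 0.106 | 52% | 0.731 |

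If individual half-lives are spread evenly over 52–76 h, the mean log bias is 0.072 (7.5%) and coverage is 0.820. With an SD of 0.20 to 0.30, coverage at 52, 64 and 76 h is 0.86–0.88, 0.79–0.85 and 0.66–0.79.

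**Milder cases (inputs assumed, not in the documents).**

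| Case | Inflation | Coverage at SD 0.24 |
|---|---|---|
| Induction to an AUCinf ratio of 0.80, complete from Period 2 Day 1: r = 2^(−72/h) × 2^(−168/(0.8h)) | 2.3% (52 h) to 7.6% (76 h) | 0.89 to 0.82 |
| Distribution phase (half-life 5 h) holding 25–50% of AUCinf | 1.6% to 6.6% | 0.90 to 0.84 |
| Both together | 0.8% to 4.4% | 0.90 to 0.87 |

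The 11.2% is the top of the stated half-life range, not a strict bound: slow absorption (rate 0.3 per h, assumed) takes it to about 12%.

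**Carry-over beside truncation.** Take a true AUCinf ratio of 0.80 as an illustration. The ratio of AUC to 72 h without carry-over is 0.8 × (1 − 2^(−72/(0.8h)))/(1 − 2^(−72/h)), which is 0.906 at 52 h and 0.930 at 76 h. These are log shifts of ln(0.906/0.80) = 0.125 and ln(0.930/0.80) = 0.151. Carry-over then raises the ratios to 0.93–0.94 and 1.00–1.04; the lower value has induction from Period 2 Day 1 and the upper has late onset. A true ratio of 0.50 would still show: 0.69–0.76 without carry-over and 0.69–0.84 with it.

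**Is there a correction elsewhere?** SAP 6.3.1 specifies standard noncompartmental methods. SAP 5.6 and 7.3 allow data or known biased individual estimates to be left out, but every Day 8 efavirenz AUC is affected, so exclusion would remove the Test condition. The concentration listing in SAP 8.2 displays the residue without changing the ratio.

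**Does subtraction work if kel is wrong?** After subtracting the residue with an incorrect half-life, the null ratio is 1.014 (truth 76 h, used 52 h) or 0.994 (truth 52 h, used 76 h), against 1.112 and 1.041 uncorrected.

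**The case against.** The strongest reply is about size. The 4–11% range needs no induction and strictly mono-exponential decay, and its upper end needs an average half-life of 76 h. Induction that starts early also clears the old residue faster, so the masking argument and the 11% figure do not belong to the same scenario unless onset is late. In the mildest cases coverage is barely affected. This stands, and it is why the range has to be read with its conditions. It also argues for measuring the residue with the predose sample instead of assuming that it is negligible.

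Second, the study is for estimation: Protocol 9.1 and SAP 4.1 and 4.2 set no hypotheses and no decision rules. This is correct. The harm is a shifted estimate and an interval that covers less often than stated, not a wrong formal decision.

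Third, truncation at 72 h usually attenuates more, and a perfect carry-over correction would still report 0.91–0.93 for a true 0.80. This is also correct, but both push an induction ratio towards 1, so they compound.

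Fourth, anyone with the listings could subtract the residue later. No data are lost, but the choice would then be made after the predose values had been seen.

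Finally, parts of the PK text are redacted, so a correction could sit there. The claim covers the visible text only.

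**Conclusion.** The concern holds. On the schedule and half-life that the protocol itself gives, the planned analysis biases the efavirenz Test/Reference ratio, a primary endpoint, upwards. The size is 4.1% to 11.2% under no induction and mono-exponential decay, and about 1% to 8% under the milder assumed cases. The arithmetic rests on the 52–76 h half-life, the 240 h interval and equal doses; the coverage figures rest also on the SD of 0.24. A strong induction effect would remain visible, while a weak one could be moved close to 1. This should be fixed: the bias is systematic, and the sample needed to address it is already in the schedule.

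**What to change.** Add to SAP 6.3.1 and 7.3 a prespecified sensitivity analysis, reported with its 90% CI beside the uncorrected result:

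- Compute the efavirenz Day 8 AUC after subtracting C_predose × exp(−kel × t) from each post-dose concentration. Use the participant's Day 8 terminal kel, or the Period 1 kel if that cannot be estimated.
- Because 72 h of sampling may not support kel, also show the result with kel fixed at half-lives of 52 h and 76 h.
- Where predose is below the limit of quantification, subtract nothing, state the limit, and repeat with predose set to the limit. The two results show the largest inflation that could remain.
- State beside the table that truncation at 72 h is not corrected.

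The cost is one SAP paragraph, a few lines of code and one table, with no new samples, visits or participants. The main limit is assay sensitivity, which the documents do not give. Without subtraction, a predose value below the limit leaves inflation of at most about LLQ/Cmax, for example 2% if the LLQ is 2% of Cmax. In a null simulation (12 participants, SD 0.24, 10% assay error), the mean ratio went from 1.076 to 0.994 with the LLQ at 2% of Cmax. With the LLQ at 10% of Cmax, 75% of predose values were below it; the ratio went from 1.085 to only 1.053, or 0.980 with predose set to the LLQ, and corrected coverage was 0.86.

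Keeping this as a sensitivity analysis leaves the primary definition unchanged. Making the corrected AUC primary would require an amendment, since Protocol section 9 says that "any major modifications of the primary endpoint definitions or their analyses will also be reflected in a protocol amendment".
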